8.1 Primary Efficacy Analysis

The primary endpoint is the change in total ear hearing assessments between baseline and 6 months, and will be assessed using the intent–to–treat population. At baseline and at 6 months, hearing thresholds (in decibels) will be determined using age–appropriate and developmentally–appropriate audiologic assessments. The decibel hearing thresholds in each ear classified whether the ear has normal hearing, mild hearing loss, moderate hearing loss, or severe hearing loss. Based on the hearing assessment of each ear at Month 6 and at Baseline, change in each ear

will be categorized into binary outcomes: improved or no change versus other. For example, normal in the left ear at baseline and moderate in the same ear at Month 6 will be considered as worsened. This binary outcome will be analyzed using logistic regression based on generalized estimating equations (GEE) in order to accommodate the correlation between the left and right ears of a subject in the modeling. In addition, if there are enough data available we will adjust the analyses by whether or not a subject at birth is asymptomatic or symptomatic from their congenital CMV infection. Additional analyses will be performed to adjust for age and site plus any imbalances in the demographic and clinical characteristics to determine if adding them to the model will impact the results. P-values < 0.05 will be considered significant for the primary outcomes.

A single, independent study audiologist who is masked (blinded) to treatment assignment will assess the audiology test battery for each subject and assign the classifications of normal hearing, mild hearing loss, moderate hearing loss, or severe hearing loss based upon their hearing thresholds (in decibels). The classifications will be assigned by ear (one for the left ear and one for the right ear), giving “total ear” classifications. , At the analyses stage, the “best ear” classification for the subject at that study visit will be determined; for example, if a subject had mild hearing loss in their left ear and severe hearing loss in their right ear, then the “best ear” classification will be mild hearing loss.

Primary analyses will be done on the first 54 subjects recruited. If there were subjects enrolled as replacement for dropouts or missing outcome, these added subjects will be included in the secondary analyses.

For those with missing outcome due to missing baseline and/or Month 6 audiology (including dropouts), we will exclude them from the primary analysis. However, we will perform sensitivity analysis by replacing all missing data with “worsening” outcome.

For those study subjects proceeding to cochlear implantation during the course of the study, he/she will not require additional study-related hearing assessments following the implantation procedure. Efficacy analyses will utilize “severe” as final hearing assessment at Month 6 for those who underwent cochlear implantation.

The summary statistics will be produced in accordance with section 7.

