## **5.4. Treatment Assignment Procedures**

### **5.4.1. Randomization Procedures**

Randomization on the study occurs when the diagnosis of congenital CMV infection is confirmed, and the subject then is assigned to either receive 6 weeks of oral valganciclovir or 6 weeks of placebo. Study subjects will be stratified according to age at randomization (1 through 11 months, 12 through 23 months, 24 through 35 months, and  $\geq 36$  months) and CMV involvement (symptomatic and asymptomatic at birth) as a marker of disease severity. Age stratification is justified by the differences in the hearing assessments methods utilized for infants younger than 12 months versus toddlers 12 months and older. Dropouts and subjects with audiology assessments that are inadequate for study comparison will be replaced (up to 20%, or n=10).

Randomization will be implemented by the web-based randomization system developed and maintained at the UAB Biostatistics Unit at the University of Alabama at Birmingham. The generation and maintenance of study randomization codes will be the responsibility of the UAB Biostatistical Unit. The codes will be kept in a secure location in the Biostatistics Unit.

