## **11.4. Final Analysis Plan**

### **11.4.1. Primary Outcome**

Primary analysis will be based on intent-to-treat population. Categories utilized for hearing assessment of each ear for each time point are normal hearing, mild hearing loss, moderate hearing loss, and severe hearing loss. Based on the hearing assessment of each ear at Month 6 and at Baseline, change in each ear will be categorized into binary outcomes: improved + no change versus other (i.e., worsened). For example, normal in the left ear at baseline and moderate in the same ear at Month 6 will be considered as worsened. The primary outcome will be analyzed using logistic regression based on generalized estimating equations (GEE) in order to accommodate the correlation between the left and right ears of a subject in the modeling. In addition, if there are enough data available we will adjust the analyses by whether or not a subject at birth is asymptomatic or symptomatic from their congenital CMV infection. Additional analyses will be performed to adjust for age and site plus any imbalances in the demographic and clinical characteristics to determine if adding them to the model will impact the results. P-values < 0.05 will be considered significant for the primary outcomes.

A single, independent study audiologist who is masked (blinded) to treatment assignment will assess the audiology test battery for each subject and assign the classifications of normal hearing, mild hearing loss, moderate hearing loss, or severe hearing loss based upon their hearing thresholds (in decibels). The classifications will be assigned by ear (one for the left ear and one for the right ear), giving “total ear” classifications. Following this, the study audiologist will assign the “best ear” classification for the subject at that study visit; for example, if a subject had mild hearing loss in their left ear and severe hearing loss in their right ear, then the “best ear” classification will be mild hearing loss.

Primary analyses will be done on the first 54 subjects recruited. If there were subjects enrolled as replacement for dropouts or missing outcome, these added subjects will be included in the secondary analyses.

For those with missing outcome due to missing baseline and/or Month 6 audiology (including dropouts), we will exclude them from the primary analysis. However, we will perform sensitivity analysis by replacing all missing data with “worsening” outcome.”

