- g) Valganciclovir or placebo administration begins on Day 1 of the study; study medication dose adjusted for weight change, if needed, at each study visit while on treatment

Hearing assessments at each time point and at each ear as well as the change in the best ear comparing Month 6 with baseline will be provided by a single Independent Audiologist (IA) who will interpret the audiology reports of all patients at all protocol-specified visits requiring hearing assessments. The IA will enter the data directly to the eDES.

Section 3.3 describes the derived variables and the techniques and rules used to obtain the transformed data that will be used in the analyses

5 Sample Size

(ICH E3; 9.7.2. ICH E9; 3.5)

The planned enrollment is 54 subjects. Dropouts and subjects with audiology assessments that are inadequate for study comparison will be replaced (up to 20%, or n=10).

A sample size of 54 (27 in each arm) has 90% power to detect a worsening of hearing from 40% to 8.0% in the treatment group based on analyzing two correlated binary outcomes with correlation coefficient of 0.55 at 2.5% level of significance (using PASS 2008 program).

6 General Considerations

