6.3 Covariates and Subgroups

(ICH E3; 9.7.1, 11.4.2.1. ICH E9; 5.7)

The primary outcome will be analyzed using logistic regression based on generalized estimating equations (GEE) in order to accommodate the correlation between the left and right ears of a subject in the modeling. In addition, if there are enough data available we will adjust the analyses by whether or not a subject at birth is asymptomatic or symptomatic from their congenital CMV infection. Additional analyses will be performed to adjust for age and site plus any imbalances in the demographic and clinical characteristics to determine if adding them to the model will impact the results.

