8.2 Secondary Efficacy Analyses

Logistic analyses will be utilized to determine if there is treatment effect based on the best ear outcome. As in the total ear analysis, change in the best ear will be categorized into binary outcomes – namely: improved + no change versus worse; improved + no change (normal to normal) versus worse + no change (abnormal to

abnormal); and improved versus other between baseline and Study Month 6. In addition to the primary outcome, we will analyze the binary outcome for change in the total ears categorized as: improved+ no change (normal to normal) versus worse and improved vs other.

For other secondary and tertiary outcomes, Fisher's exact test will be used to compare binary outcomes (such as detection of viruria or subject with at least one AE or SAE), and Wilcoxon Rank test will be used to compare continuous outcomes (such as quantitative log reduction) between the two treatment groups 6 weeks and 6 months after initial treatment.

Logistic model utilizing generalized estimating equations will also be used to determine the association between change in hearing and change in viral load. Change in viral load over time will be measured by the area under the curve computed using the trapezoidal rule. Spearman rank correlation will be utilized to examine the association between viral load and PK parameters. Poisson regression model will be used to compare the number of AEs/SAEs experienced by subjects between the two groups.

As in the primary outcomes, missing change in hearing outcomes will be replaced by worsened outcomes as sensitivity analyses for all secondary hearing outcomes.

The summary statistics will be produced in accordance with section 7.

9 Safety Analyses

Analyses of safety data will be based on data from all subjects receiving at least one dose of study drug. As per protocol, safety data will be collected only through Study Day 70, i.e., four weeks after the last study dose.

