| Table 18b: Weight (kg) at the Time of Dosing of Valganciclovir or Placebo | 18b | At least one dose of study drug | Dose | Day 1, 14 28 | Therapy Group, Visit | N, Mean, SD, Median, Min, Max | General linear mixed model with random intercept was fitted for each parameter. Each model contains therapy, time and therapy by time interaction. |
| Table 18c: Length (cm) at the Time of Dosing of Valganciclovir or Placebo | 18c | At least one dose of study drug | Weight | Day 1, 14 28 | Therapy Group, Visit | N, Mean, SD, Median, Min, Max | General linear mixed model with random intercept was fitted for each parameter. Each model contains therapy, time and therapy by time interaction. |
| Table 19a: Dosing Administration by Treatment Group and Visit | 19 | At least one dose of study drug | Length | Day 1, 14 28 | Therapy Group, Visit | n, % | Fisher's exact |
| Table 19b: Reasons for Adjusted or Held Dose and Significant Changes in Laboratory Parameters | 19a | At least one dose of study drug | Dose | Day 1, 14 28 | Therapy Group, Visit | n, % | Fisher's exact |
| Table 20: PK Specimen Results: GCV concentration in the Active Group | 19b | At least one dose of study drug | Dose | Day 1, 14 28 | NA | N, Mean, SD, Median, Min, Max | NA |
| Table 21a: Quality of Hearing Assessment Left and Right (Total Ear) | 20 | At least one dose of study drug | GCV concentration | Day 14, 28, 42 | NA | n, % | NA |
| Table 21b: Hearing Assessment Left and Right (Total Ear) | 21a | At least one dose of study drug | Quality of Total Ear Assessment | Baseline and Month 6 | Therapy Group, Visit | n, % | NA |
| Table 21c: Change in Total Ear Hearing at Month 6 Relative to Baseline | 21b | At least one dose of study drug | Hearing Assessment Total Ear | Baseline and Month 6 | Therapy Group, Visit | n, % | NA |

| | | | | | | | |
|---|-----|---------------------------------|--|----------------------|--|-----------------------------------|---|
| Table 21d: Results of Modeling Treatment Effect on Total Ear For Each Outcome | 21c | At least one dose of study drug | Change in Total Ear Hearing Assessment | Baseline and Month 6 | Therapy Group | n, %, p-value | Generalized linear model for binary outcome using GEE was fitted for each parameter. Each model contains therapy, time and therapy by time interaction. |
| Table 21e: Subgroup Analysis (Total Ears) | 21d | At least one dose of study drug | Change in Total Ear Hearing Assessment | Baseline and Month 6 | Therapy Group | n, % | NA |

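### The primary GEE does not commit to adjusting for the randomization strata, has no method for an arm without worsened ears, and two table rows list time terms that cannot be estimated

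*SAP*

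**What the plan says.** Protocol 5.4.1 stratifies randomization by age in four bands and by symptomatic or asymptomatic infection at birth. It justifies the age strata by "differences in the hearing assessments methods utilized for infants younger than 12 months versus toddlers 12 months and older".

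Protocol 11.4.1, SAP 6.3 and SAP 8.1 analyze the binary per-ear outcome (worsened or not) by logistic GEE. On symptom status, SAP 8.1 says that "if there are enough data available we will adjust the analyses by whether or not a subject at birth is asymptomatic or symptomatic". On the rest, Protocol 11.4.1 says "Additional analyses will be performed to adjust for age and site plus any imbalances in the demographic and clinical characteristics". The 0.05 criterion follows without saying which fit it governs. No working correlation, variance correction or method for an arm without worsened ears is given.

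Missing outcomes reduce the primary set: "For those with missing outcome due to missing baseline and/or Month 6 audiology (including dropouts), we will exclude them from the primary analysis". That analysis uses the first 54 recruited, and replacements enter only secondary analyses.

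For the best ear, SAP 8.2 says "Logistic analyses will be utilized to determine if there is treatment effect based on the best ear outcome". In SAP 17, the rows titled Table 21d (total ear) and Table 22d (best ear) both read "Generalized linear model for binary outcome using GEE was fitted for each parameter. Each model contains therapy, time and therapy by time interaction". The Number column there is one row out of step, so I cite rows by title.

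**The concern.** Factors important enough to stratify on would normally be in the primary model. If they predict worsening, leaving them out makes the usual test too cautious. A clause that depends on the amount of data, without a threshold, also invites a decision made with outcomes in view, and the study statistician is not masked (Protocol 5.4.2).

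The sparse-data gap matters in its own right. The trial hopes for very few worsened ears on active drug, and zero is the case in which a logistic model has no finite odds ratio. The study behind the design had 0 of 25 best-ear worsenings on ganciclovir (Protocol 2.1.2.1).

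The time terms matter because SAP 14 assigns Tables 21d and 22d to a second statistician for independent reproduction, and that model cannot be fitted as written.

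**Working it through.** **1. The plan's power.** SAP 5 gives 27 children per arm, 40% versus 8% worsening, and "two correlated binary outcomes with correlation coefficient of 0.55 at 2.5% level of significance". With two ears per child, the effective number per arm is 54 / (1 + 0.55) = 34.8. The pooled two-proportion formula gives 89.6% at one-sided 2.5% (two-sided 5%) and 83.0% at two-sided 2.5%. The stated 90% is therefore reproduced with 2.5% read as one-sided, which agrees with p < 0.05. No covariate enters this calculation.

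**2. Information available.** There are 4 × 2 = 8 strata, so 54 / 8 = 6.75 children each. Expected worsened ears are 54 × 0.40 + 54 × 0.08 = 25.9, or 44 × 0.48 = 21.1 with 22 children per arm.

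**3. An arm with no worsened ear.** At 8% and correlation 0.55, the chance that neither ear of a child worsens is 0.92² + 0.55 × 0.08 × 0.92 = 0.887. For the whole active arm it is 0.887^27 = 3.9%, or 0.887^22 = 7.1% with 22 children. In a simulation with no stratum effects, the unadjusted Wald test rejected in 88.9% of trials where the fits converged, and its fit failed in 64 of 2,000. So 0.889 × (1 − 64/2,000) = 86%. A robust score test, which fits only the null model, gave about 90 to 91%.

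**4. Effect of adjustment.** Simulation: 20,000 null trials and 10,000 per power scenario. Assumed, not in the documents: eight equally likely strata, permuted blocks of 4, every ear able to worsen, and an odds ratio of 1, 2 or 4 for each of symptom status and age (under versus at least 12 months). Both tests are robust score tests with independence working correlation and variance multiplied by n/(n − k), k = 3 adjusted and 1 unadjusted. The SAP specifies neither feature, so the unadjusted rows favour the plan relative to a Wald test.

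| Scenario | Test | OR 1 | OR 2 | OR 4 |
|---|---|---|---|---|
| 40% in both arms, 54 children | unadjusted | 5.2% | 4.3% | 3.1% |
| | adjusted | 5.2% | 5.0% | 4.8% |
| 40% vs 8%, 54 | unadjusted | 90.7% | 90.8% | 91.2% |
| | adjusted | 90.5% | 91.4% | 93.6% |
| 40% vs 15%, 54 | unadjusted | 66.1% | 65.3% | 65.4% |
| | adjusted | 65.6% | 66.9% | 72.4% |
| 40% vs 15%, 44 | unadjusted | 56.3% | 55.2% | 54.9% |
| | adjusted | 55.2% | 56.8% | 61.6% |

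A separate simulation at OR 4 gave 3.4% type I error unadjusted, and power at 40% vs 15% of 65.6% unadjusted and 71.5% adjusted. The gain is thus 5.9 to 7.0 points at OR 4. At OR 1 the cost is up to 1.1 points (56.3 − 55.2, with 44 children).

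The adjusted rows reverted to the unadjusted test when an arm had no worsened ear. This hardly matters: in such trials at the planned effect both tests had p < 0.05 every time (unadjusted 106 of 106 with 54 children; adjusted 173 of 173 at OR 1 and 153 of 153 at OR 4).

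**5. Are the strata prognostic?** The table in Protocol 2.1 shows progressive loss in 46/85 symptomatic and 26/48 asymptomatic children with hearing loss. The odds ratio is (46 × 22)/(39 × 26) = 1.00, 95% CI 0.49 to 2.03. These are long-term data, not six-month data.

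**6. Age levels.** With two age levels the covariate model could not be fitted in 0.2 to 0.9% of trials at the planned effect (54 children), against 3.4 to 7.5% with four. In an uneven mix (70% symptomatic, half under 12 months; OR 1 and 4) the figures were 0.3% and 6.3%, against 14.9% and 46.1%.

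**7. Time terms.** Hearing is assessed at baseline and Month 6, so there is one change value per ear or per child. Time is then constant: it duplicates the intercept, and therapy-by-time duplicates therapy. The design matrix has 4 columns and rank 2.

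**The case against.** The main objection is that the plan already has a primary model. It names logistic GEE first and brings in the covariates as additions, to see whether they change the result. That stands: the natural reading is that the unadjusted GEE is primary, and one sentence would confirm it.

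A reader might infer that the loose clause inflates type I error. The calculations do not support this to any real extent. Under the assumptions of step 4, at OR 1 and 4, taking whichever of the unadjusted, symptom-adjusted and symptom-plus-age tests is significant gives 5.7% and 5.7% (uncorrected Wald) or 5.3% and 5.1% (corrected score). Stronger stratum effects and all four age levels with uncorrected variance gave 6 to 7%, but there the fully adjusted test alone already ran at 5.7 to 7.0%.

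It is also fair that adjustment is no certain gain. The one relevant figure in the documents shows no difference by symptom status, and the 6 to 7 points require an assumed odds ratio of 4 for both factors. Collapsing age to two levels does not reproduce the stated strata either, so it must be declared as a collapse. The row titled Table 22e names age and symptom status as subgroups, but subgroup counts do not replace adjustment of the primary test.

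Finally, the time terms look like text carried over from the repeated-measures rows. SAP 8.1 and 8.2 contain none, and without them the therapy-only model remains. They do not show that the primary analysis itself cannot be run.

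**Conclusion.** The point holds at minor to moderate severity. The plan stratifies on two factors and does not commit its primary test to either. The unadjusted test does not inflate type I error, and a corrected score test loses little power at the planned 40% versus 8%. The loss of about 6 to 7 points appears at a smaller effect (40% versus 15%) and only if both factors are strongly prognostic, which the documents do not establish.

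The zero-event gap is firmer because it follows from the plan's own rates and correlation: 3.9% of trials, or 7.1% if 10 of the first 54 children are not evaluable (assumed equally across arms). If the GEE is tested by Wald, which the SAP does not say, power is about 86%.

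The time terms are wrong as written. It would be too strong to say that the plan has no primary model or that its stated power is wrong: the model family is named, and the 90% is reproduced at one-sided 2.5%.

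**What to change.** In SAP 6.3 and 8.1 and Protocol 11.4.1:

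- Name the primary model: GEE with therapy, symptom status at birth and age under versus at least 12 months, declared as a collapse of the four strata on the rationale in Protocol 5.4.1. Use independence working correlation.
- Test therapy by a robust score test with a stated small-sample correction and a defined parameter count. For n/(n − k), n could be evaluable children and k the parameters of the null model including the intercept: 3 adjusted, 1 unadjusted.
- Keep the adjusted score test when an arm has no worsened ear, and change only the estimate to a stated exact or penalized odds ratio. An exact odds ratio for any worsened ear per child is one option, labelled child-level; 0/27 versus 14/27 gives an upper 95% bound of 0.18. Inverting the robust score test will not serve: it gave no bound in 106 of 106 such trials.
- Use the unadjusted score test only if the null covariate model cannot be fitted, with that condition defined. This replaces the clause "if there are enough data available we will adjust the analyses".
- Report the unadjusted GEE as a sensitivity analysis, and keep site and observed-imbalance adjustments exploratory.

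In SAP 17, delete the time and therapy-by-time terms from the rows titled Table 21d and Table 22d.

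The cost is wording; both factors are already needed at randomization. The downsides are two extra parameters with about 26 expected worsened ears, or fewer because an ear already in the severe category cannot worsen; up to about 1 point of power if the strata are not prognostic; and 5.5 to 5.9% type I error if the small-sample factor is omitted. The adjusted odds ratio is also conditional on the strata, so it need not equal the unadjusted one.

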3.3 Derived variables

The primary efficacy assessment will be change in total ear hearing assessment between baseline and 6 months post enrollment. Categories used for hearing assessment of each ear for each time point will be normal hearing, mild hearing loss, moderate hearing loss, and severe hearing loss. Baseline and 6 month hearing categories will be compared and the change in each ear will be categorized into binary outcomes: Improved or no change versus Other (i.e., worsened) Note that the total ear assessment at each time point will be provided by the Independent Audiologist and entered in the database following the rules below and the information provided by the audiology reports.

In the model-based analyses, the “no change” category will be broken down into “Protected: normal to normal” as one category and “No Change: same degree of hearing loss at Baseline and Study Month 6” as another category. The rationale behind this is that if one is interested in the improvement of hearing loss, a subject that has normal hearing at baseline cannot improve further. Hence from an efficacy analysis point of view, the “Protected: normal to normal” can be viewed as protective effect of the drug from hearing deterioration. This analysis approach will be similar to the analysis of the previous CASG study that established the efficacy of 6 weeks of IV GCV in symptomatic congenital CMV disease with CNS involvement.

Analysis of actual viral load will be done using log base 10 transformation. Undetectable viral load value will be replaced by a value of 10. A summary measure of the viral load over time will be calculated two ways. The first approach considers all time points available by calculating the average area under the curve (AUC) (trapezoidal rule) applied to the log base 10 viral load. Average is based on the maximum period of time with viral load data for a given subject. To illustrate, if the calculated AUC for log₁₀ VL for a given subject is 200 from baseline to Day 70, then average AUC is $200/70=2.86$. Taking average AUC will enable us to use and compare data from subjects who did not have viral load values at the later time due to dropping out early, for example, with subjects with complete viral load data. The second approach is to take using difference between Month 6 and baseline log₁₀ VL. The last visit with available VL will be used for those without Month 6 VL. Section 11 contains more details on Viral Load analyses.

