4.3 Inclusion–Exclusion Criteria and General Study Population

(ICH E3;9.3. ICH E9;2.2.1)

Male and female infants from 1 month through 3 years of age (up to 4th birthday) with sensorineural hearing loss will be eligible for enrollment. Following confirmation of inclusion/exclusion criteria and the signing of informed consent, the subject's Guthrie card will be retrieved and tested for CMV DNA by PCR unless there is a virologically confirmed diagnosis of congenital CMV infection made within the first 30 days of life. Inclusion criteria were selected to ensure the inclusion of those subjects with congenital CMV disease. Exclusion criteria were selected to limit confounders for safety and efficacy. Renal insufficiency was an exclusion criterion because the active moiety, GCV, is renally cleared and a neonate's renal system is not fully developed. The study population is consistent with those patients seen in clinical practice and who receive IV GCV as standard of care to treat symptomatic congenital CMV.

Inclusion Criteria

- Signed informed consent from parent(s) or legal guardian(s)
- Sensorineural hearing loss (≥ 21 dB in one or both ears, documented within 12 weeks prior to study entry)
- Children from 1 month through 3 years of age (up to the 4th birthday)
-

Exclusion Criteria

- Imminent demise
- Profound sensorineural hearing loss (> 90 dB) in both ears
- Patients receiving other antiviral agents or immune globulin
- Gastrointestinal abnormality which might preclude absorption of an oral medication (e.g., a history of necrotizing enterocolitis)
- Documented renal insufficiency, as noted by a creatinine clearance < 10 mL/min/1.73m² at time of study enrollment
- Breastfeeding from mother who is receiving ganciclovir, valganciclovir, foscarnet, cidofovir, or maribavir
- Infants known to be born to women who are HIV positive (but HIV testing is not required for study entry).
- Current receipt of other investigational drugs
- Previous receipt of ganciclovir or valganciclovir

- Known hypersensitivity to ganciclovir, valganciclovir, or components of the product
- Inability to attend follow-up hearing and clinical assessments
- Infants with Auditory neuropathy/dyssynchrony.
- Children with another known etiology for SNHL (e.g. connexin 26, syndrome or metabolic disorder associated with SNHL, inner ear malformation and widened vestibular aqueducts, meningitis). Exclusion of each of these conditions is not required for trial enrollment.

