7.2 Protocol Deviations

Protocol deviations will be summarized by site and type of deviation; deviations that resulted in adverse and serious adverse events; and protocol deviations that resulted in termination. The summary statistics will be produced in accordance with Section 7.

A raw listing of all protocol deviations will be provided by site by subject ID, deviation date, resulting in AE, SAE, and termination; deviation description; reason for the deviation; deviation category; effect on product stability; and deviation resolution.

As per protocol, if a study subject proceeds to cochlear implantation during the course of the study, he/she will not require additional study-related hearing assessments following the implantation procedure. Hence, hearing outcomes from these subjects past implantation will not be included in the analyses.

Finally, any subjects enrolled but not eligible will also be excluded from the analyses.

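### The SAP's two cochlear-implant rules (7.2 and 8.1) are not linked, and the 8.1 rule is written per child although the primary outcome is scored ear by ear

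*SAP*

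**What the plan says.** SAP 7.2 (Protocol Deviations) notes that an implanted child needs no further study hearing assessments, then states: "Hence, hearing outcomes from these subjects past implantation will not be included in the analyses". Its next sentence says that enrolled but ineligible subjects are also excluded.

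SAP 8.1 (Primary Efficacy Analysis) repeats the point about further assessments and then states: "Efficacy analyses will utilize “severe” as final hearing assessment at Month 6 for those who underwent cochlear implantation". Neither section refers to the other. The statistical section of the protocol (section 11) has no implant rule.

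The unit of assessment is the ear. SAP 8.1: "The classifications will be assigned by ear (one for the left ear and one for the right ear), giving “total ear” classifications". SAP 4.5 likewise has the independent audiologist provide "Hearing assessments at each time point and at each ear as well as the change in the best ear". The binary outcome (improved or no change against worsened) is formed for each ear, and the GEE model treats ears as clustered within the child. A child can enter with one affected ear: SAP 4.3 asks for loss of at least 21 "dB in one or both ears, documented within 12 weeks prior to study entry".

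Two other rules bear on this. The ITT set (SAP 6.2) requires completed hearing data at baseline and Month 6. SAP 8.1 excludes missing outcomes from the primary analysis and adds: "However, we will perform sensitivity analysis by replacing all missing data with “worsening” outcome".

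**The concern.** There are two gaps.

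- **Which rule applies.** If 8.1 governs, the implanted child is in the primary analysis with an assigned value, and the missing-as-worsened run does not touch it. If 7.2 is read alone, the child has no Month 6 outcome, leaves the ITT set and the primary analysis, and reappears as worsened only in the sensitivity run. Two programmers could therefore build different primary data sets.
- **Which ear it applies to.** The 8.1 rule speaks of subjects. Followed literally, it overwrites the result of an ear that was never implanted. If that ear was normal, mild or moderate at baseline, it is scored as worsened even when its hearing did not change.

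With 27 children per arm, a borderline result could depend on one child. If the choice were made after unmasking, it would be a post hoc choice.

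**Working it through.** **1. The readings side by side.** Take a child with one moderate ear, later implanted, and one normal ear that stays normal.

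| Reading | Implanted ear | Other ear | Best ear |
|---|---|---|---|
| 8.1, implanted ear only | worsened | no change | normal, no change |
| 8.1, literal (per child) | worsened | worsened | severe, worsened |
| 7.2 alone, with ITT and missing-outcome rules | child removed | child removed | child removed |

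**2. The design figure.** The inputs are 27 children per arm, worsening of 40% against 8%, between-ear correlation 0.55 and a 2.5% level (SAP 5). Effective ears per arm: 2×27/(1+0.55) = 34.84. Reading the level as one-sided 2.5%, with pooled variance and mean rate 0.24:

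z = [0.32×√34.84 − 1.96×√(2×0.24×0.76)] / √(0.40×0.60 + 0.08×0.92) = (1.889 − 1.184)/0.56 = 1.26, so power is 89.6%.

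The stated 90% is reproduced. Nothing in this point disputes it. The design rates correspond to about 22/54 and 4/54 worsened ears. One ear is 1/54 of an arm, or 1.9 percentage points.

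**3. Illustrations.** The documents give no implant numbers, so every count here is assumed and chosen to lie near p = 0.05. The model is logit P(ear worsened) = β0 + β1×active, fitted by GEE with exchangeable correlation within child and a robust Wald test of β1. With two ears per child the odds ratio is the crude one, for example (4/50)/(14/40) = 0.229. The last column uses a bias-reduced sandwich variance; the SAP does not name an estimator.

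The underlying counts, as children with both / one / no ears worsened, are:
- A and D: active 1/2/24; other 26 placebo children 4/4/18.
- B and E: other 26 active children 0/2/24; placebo 4/4/19.
- C: other 26 active children 1/1/24; placebo 5/4/18.

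| Case | Rule | Active | Placebo | OR | p | p, bias-reduced |
|---|---|---|---|---|---|---|
| A. Placebo child, both ears moderate and both set to severe | 8.1 | 4/54 | 14/54 | 0.229 | 0.0466 | 0.0553 |
| | 7.2 alone | 4/54 | 12/52 | 0.267 | 0.0784 | 0.0902 |
| B. Same child in the active arm | 8.1 | 4/54 | 12/54 | 0.280 | 0.0897 | 0.1022 |
| | 7.2 alone | 2/52 | 12/54 | 0.140 | 0.0161 | 0.0206 |
| C. Active child, moderate implanted ear, other ear normal and unchanged | 8.1 by ear | 4/54 | 14/54 | 0.229 | 0.0466 | 0.0553 |
| | 8.1 per child | 5/54 | 14/54 | 0.292 | 0.0959 | 0.1088 |
| D. As A, one ear implanted, other unchanged | 8.1 by ear | 4/54 | 13/54 | 0.252 | 0.0622 | 0.0726 |
| | 7.2, child removed | 4/54 | 12/52 | 0.267 | 0.0784 | 0.0902 |
| | 7.2, ear removed | 4/54 | 12/53 | 0.277 | 0.0868 | 0.0992 |
| E. As B, one ear implanted, other unchanged | 8.1 by ear | 3/54 | 12/54 | 0.206 | 0.0255 | 0.0315 |
| | 7.2, child removed | 2/52 | 12/54 | 0.140 | 0.0161 | 0.0206 |
| | 7.2, ear removed | 2/53 | 12/54 | 0.137 | 0.0148 | 0.0189 |

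Cases A and B cross 0.05 only because both ears of the child are rescored, by bilateral implantation or by the per-child wording. With one implanted ear (D and E) the choice between 7.2 and 8.1 does not cross. Case C crosses with one untouched ear. Under the bias-reduced variance, A and C no longer cross; B still does.

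**4. Near the design rates.** Let the other 26 placebo children be 7/8/11, giving 22/52, with active 4/54. Case A then gives 24/54 (p = 0.0011) under 8.1 and 22/52 (p = 0.0018) under 7.2. Case C against 24/54 gives p = 0.0011 by ear and 0.0035 per child. The conclusion is the same each time.

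**The case against.** The strongest reply is that 8.1 is the specific efficacy rule and 7.2 sits under protocol deviations, so 8.1 governs. On this view 7.2 discards measured post-implant values, 8.1 states what replaces them, and an ear-level analysis would naturally apply the value to the implanted ear only. Much of this stands. A reader might infer that the two sections flatly contradict each other. The text does not require that, since they can be read together. What is missing is any statement that they should be. The word 'also' in the next sentence of 7.2, together with the ITT and missing-outcome rules, gives real support to the exclusion reading. For the per-child wording, the sensible reading likewise has to be supplied by the reader.

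A second tempting inference is that the rule is faulty because an implanted ear already severe at baseline scores as no change, a favourable result, and is not reached by the missing-as-worsened run. This is a general limit of the prespecified scale. No change for an abnormal ear means the "same degree of hearing loss at Baseline and Study Month 6", so every stable severe ear scores this way, implanted or not. SAP 3.2 lists a total-ear secondary outcome that groups worse with unchanged abnormal ears, and SAP 3.3 splits no change into protected and same degree of loss. Neither is an implant-specific sensitivity run, but the plan does look at such ears unfavourably elsewhere.

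**Conclusion.** The point holds as a defect of specification. SAP 7.2 and 8.1 do not say how they fit together, and 8.1 taken literally scores a non-implanted, unchanged ear as worsened whenever it began better than severe.

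The size is unknown and may be nil, because the documents give no implant count. A p-value crosses 0.05 only for a near-threshold result, under assumed counts, and either through both ears of one child (placebo 0.047 against 0.078; active 0.090 against 0.016) or through the per-child wording applied to one untouched ear (0.047 against 0.096). The 0.047 fits become 0.055 with a bias-reduced variance. A reader might infer that the trial's conclusion depends on the implant rule; near the design rates it does not.

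It should still be settled before unmasking, because the rule decides which data enter the primary analysis.

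**What to change.** State one ear-level rule, in the same words, in SAP 7.2 and 8.1:

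- Measured post-implant values of the implanted ear are discarded.
- Severe is assigned at Month 6 to the implanted ear only.
- That assigned value counts as complete Month 6 data for the ITT definition in SAP 6.2.
- The non-implanted ear is scored on its own Month 6 data. If it has none, that ear alone is missing and the child stays in.

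Report the number of implanted ears by arm and baseline category. Optionally, add one sensitivity run that scores implanted ears already severe at baseline as worsened.

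Do not replace severe with the pre-implant audiogram sought in Protocol 8.1.4 in the primary analysis. An implanted ear that was stable at mild or moderate before implantation would then change from worsened to no change, which is a debatable change of estimand and adds favourable outcomes.

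The cost is SAP wording, a small table and at most one extra run, with no new data. The downside is that a child with one implanted ear contributes at most one measured ear. Because Protocol 8.1.4 does not require testing after implantation, the child may contribute only the assigned one.
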